1.0 TITLE OF PROPOSED PROJECT: TELEHEART: Telotristat Ethyl in a Heart Biomarker Study

TOTAL PROJECT DURATION: 56 months

EXPECTED START DATE: estimated to be 1/1/2021

EXPECTED FINISH DATE: estimated to be 8/31/2025

2.0 Objectives

The purpose of the study is to evaluate the effect of telotristat ethyl (XERMELO) + somatostatin analog (SSA) (Treatment arm) versus placebo + SSA (standard of care arm) in patients with carcinoid syndrome and carcinoid heart disease. The study will be conducted in agreement with Good Clinical Practice guidelines and the Declaration of Helsinki and be submitted for approval to the MD Anderson Cancer Center IRB before initiation.

Primary Objective:

1. To estimate the percent change in NT-proBNP at 6 month visit from baseline after initiation of study drug in each arm and to compare the percent change between the two study arms.

Secondary Objectives:

1. To evaluate the change in functional capacity from baseline at 3 and 6 month visits as assessed by a 6 minute walk test (6MWT) in each arm
2. To evaluate changes in echocardiographic parameters (CVHD score, global longitudinal myocardial strain assessment of the Left and right ventricle/TAPSE) from baseline to 3 and 6 month visits in each arm
 - a. Carcinoid Valvular Heart Disease (CVHD) score is determined by 1) tricuspid valve appearance, 2) tricuspid regurgitation severity by either spectral pulsed wave or color Doppler flow mapping; 3) pulmonary stenosis severity by spectral pulsed or continuous wave Doppler, and 4) pulmonary insufficiency severity by color Doppler. (Denney et al. JACC 1998)
 - b. Global longitudinal myocardial strain assessment will be conducted using GE Vivid echocardiography machines in all studies. Significant change will be defined as a change in global longitudinal strain by 15%.
 - c. TAPSE will be defined as normal ($\geq 1.6\text{cm}$) or abnormal ($< 1.6\text{cm}$)

3. To evaluate the change from baseline to 3 and 6 month visits in Plasma 5-hydroxyindoleacetic Acid (5-HIAA) levels in each arm. 5-HIAA is a standard test used in clinical practice to assess neuroendocrine tumor (NET) activity.
4. To evaluate the change from baseline to 3 and 6 month visits in high sensitivity troponin T in each arm
5. To evaluate the change from baseline to 3 and 6 month visits in health related quality of life with using the MD Anderson Symptom Inventory (MDASI) in each arm
6. To evaluate compliance of medications

Primary endpoint: The percent change in NT-proBNP at 6 month visit from baseline

Secondary Endpoints:

1. The change in 6MWT from baseline at 3 and 6 months
2. The change in CVHD score from baseline at 3 and 6 months , change (significant change or non-significant change) in global longitudinal myocardial strain assessment of the left and right ventricle from baseline at 3 and 6 months, change (normal or abnormal) in TAPSE from baseline at 3 and 6 months
3. The change in plasma 5-HIAA levels from baseline at 3 and 6 months
4. The change in high sensitivity troponin T from baseline at 3 and 6 months
5. The change in quality of life questionnaire (using MD Anderson Symptom Inventory (MDASI)) from baseline at 3 and 6 months
6. The proportion of patients maintaining at least 70% compliance

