3.4 Biomarkers in Carcinoid Heart Disease and Carcinoid Syndrome

While clinical signs maybe difficult to assess the role of the cardiac biomarkers has been studied and utilized in both patient with carcinoid heart disease and carcinoid syndrome. Patients with normal NT-proBNP levels have a better survival when they have carcinoid syndrome irrespective of whether or not they have carcinoid heart disease (17). Furthermore, NT-pro-BNP and 5-HIAA levels are independently associated with

symptom status and mortality in patients with metastatic NETs and carcinoid heart disease (26).

Patients with carcinoid heart disease in general have elevated NT-proBNP levels (Median 1,149 pg/ml vs 101 pg/ml) (18) highlighting the prognostic implications of this cardiac biomarker. Lastly, an NT-proBNP level cutoff of 260 pg/ml provides a high sensitivity (92%) and specificity (91%) to detect carcinoid heart disease (18). In fact this NT-ProBNP levels cutoff is being advocated in the Carcinoid Heart Disease expert statement for the screening and investigation of carcinoid heart disease (19).

As serotonin levels are implicated in both carcinoid syndrome and carcinoid heart disease, urinary 5-HIAA levels are also associated with the disease. In fact, a Urinary 5-HIAA level of $>300 \mu\text{mol}/24 \text{ hours}$ is associated with a 2.74-fold increase of the development and progression of carcinoid heart disease (20).

Furthermore, a novel echocardiographic technique, myocardial strain analysis, has some promising applications in patients with carcinoid disease. In a study using the RV free wall strain and tricuspid annular plane systolic excursion (TAPSE), it has been demonstrated that RV function is reduced in patients with intestinal carcinoid disease independent of obvious valvular involvement. This finding, in addition to the fact that patients with and without carcinoid heart disease showed slightly but significantly reduced LV global strain compared with healthy individuals, would suggest that that intestinal carcinoid disease may affect cardiac function before valvular involvement (25) and perhaps the possible role of serotonin in this process.

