11.2 Statistical Analysis Plan

We will analyze two analysis sets, including modified intention-to-treat and per protocol analysis sets. Modified intention-to-treat analysis set will include all patients who were randomized and started a study treatment, regardless of whether they received treatment as planned. Per protocol analysis set will include all patients who received treatment as planned.

Patient baseline characteristics and outcome variables (primary endpoint and secondary endpoints (absolute changes and percent changes for continuous endpoints)) will be summarized by study arm, using mean (standard deviation (SD)) or median (inter quartile range (IQR)) for continuous variables and frequency (%) for categorical variables. Repeatedly measured variables will be summarized using descriptive statistics by study arm and by time point (baseline, 3 months, and 6 months). The mean percent

change in NT-proBNP at 6 months from baseline will be estimated in each arm along with the standard deviation. The mean percent change in NT-proBNP will be compared between 2 arms by two-sample t-test. Linear regression model will be used to compare the 2 arms in the mean percent change, adjusting for stratification factors. Those without 3-months or 6-months NT-proBNP may be imputed, using last observation carried forward method or other methods.

Compliance is defined as the total number of medications taken divided by the total number of medications provided during 6 month treatment period. The proportion of patients maintaining at least 70% compliance will be estimated in each arm. Proportion of patients experiencing each type of side effects will be estimated in each arm along with 95% confidence interval (CI). The change from baseline to 3 months and the change from baseline to 6 months in variables described in secondary objectives will be compared within each arm by paired t-test or Wilcoxon signed-rank test for continuous variables and Mantel-Haenszel test for categorical variables. Generalized linear mixed effects models will be used to compare two arms in repeatedly measured outcomes over time. P-values less than 0.05 will indicate statistical significances. SAS 9.4 (Cary, NC) and other relevant software will be used for statistical analysis.

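### The TAPSE endpoint keeps only normal or abnormal at 1.6 cm, so change in centimetres is not clearly analysed and power is lost, by an amount that depends on assumptions

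*Combined protocol and SAP*

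**What the plan says.** Section 2.0, Secondary Objective 2c, classes TAPSE as normal at 1.6 cm or more and abnormal below that. Secondary endpoint 2 follows it: "change (normal or abnormal) in TAPSE from baseline at 3 and 6 months". In the same list, CVHD score, 6-minute walk distance, 5-HIAA and troponin are left as plain change. Strain, the other measure of right-ventricular function, is also categorised: "change (significant change or non-significant change) in global longitudinal myocardial strain assessment of the left and right ventricle from baseline".

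Section 11.2 has three provisions that bear on TAPSE:

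- Outcome variables are summarised by arm, including "secondary endpoints (absolute changes and percent changes for continuous endpoints".
- Within-arm change is tested by "paired t-test or Wilcoxon signed-rank test for continuous variables and Mantel-Haenszel test for categorical variables".
- Between arms, "Generalized linear mixed effects models will be used to compare two arms in repeatedly measured outcomes over time". No response scale is named for TAPSE.

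Sections 8.6, 8.7 and 8.13 schedule echocardiography at baseline and 6 months for everyone. The 3-month echo is scheduled only for the CHD group, which under 8.6 includes carcinoid syndrome patients with high suspicion of heart disease.

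**The concern.** Taken as written, the endpoint makes TAPSE a two-level variable. It then falls under the categorical provisions of section 11.2 and outside the summaries reserved for continuous endpoints. Some consequences follow from the definition alone, with no assumption:

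- 1.0 to 1.5 cm counts as no change.
- 2.4 to 1.7 cm counts as no change.
- 1.58 to 1.61 cm counts as normalised.
- From any start at or above 1.6 cm, no improvement can be recorded.

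Objective 2 is to evaluate change in the echocardiographic parameters. Because strain is categorised too, no right-ventricular function endpoint stays on its measured scale. With about 52 evaluable patients, the trial would give up information that it already collects, and an analysis in centimetres added after unblinding would be post hoc.

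**Working it through.** **The plan's own figure.** The documents give no sample size, power or expected rate for TAPSE. The only sizing, in section 11.1, is for NT-proBNP: effect size 0.8, two-sided alpha 0.05, 80% power. A two-sample t-test needs 25.5, so 26 per arm, with power 80.7%. Allowing for 13% dropout, 52/(1 − 0.13) = 59.8, so 60 enrolled. This reproduces, and 26 per arm is used below.

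**Inputs assumed, not in the documents.** TAPSE approximately normal; SD 0.4 cm; correlation ρ between baseline and 6 months of 0.6 to 0.8; true arm difference 0.25 cm; baseline mean 1.6, 1.9 or 2.2 cm. The difference may arise because treatment raises TAPSE while placebo stays flat, or because placebo falls while treatment holds it.

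**Analysis in centimetres, adjusted for baseline.** SE = SD × √[(1 − ρ²) × 2/n].

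- ρ = 0.6: 0.4 × √(0.64 × 2/26) = 0.0888; 0.25/0.0888 = 2.82; power ≈ Φ(2.82 − 1.96) = 80%.
- ρ = 0.8: 0.4 × √(0.36 × 2/26) = 0.0666; 0.25/0.0666 = 3.76; power ≈ Φ(3.76 − 1.96) = 96%.

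Simulation with the t reference gives about 77–96%, whatever the direction or baseline mean.

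**The category at 6 months.** The share abnormal in an arm is Φ((1.6 − mean)/0.4). Two tests were simulated: a plain comparison of proportions, and a Mantel-Haenszel comparison of the arms stratified by baseline category. The second stands in for a baseline-adjusted model on the category.

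| Baseline mean | How the difference arises | Abnormal, placebo / treated | Plain | Stratified |
|---|---|---|---|---|
| 1.6 cm | treatment raises | 50% / 27% | about 43% | see below |
| 1.6 cm | decline prevented | 73% / 50% | 40–43% | 47–54% |
| 1.9 cm | treatment raises | 23% / 8% | about 31% | see below |
| 1.9 cm | decline prevented | 45% / 23% | 40–43% | 46–50% |
| 2.2 cm | treatment raises | 7% / 2% | about 6% | see below |
| 2.2 cm | decline prevented | 19% / 7% | 28% | 28–29% |

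Where treatment raises TAPSE, the stratified test stays within the same overall ranges, up to simulation error. At 1.6 cm the two directions are mirror images, so the spread from 40 to 43% is simulation error around about 43%. The range of 43–54% there reflects the test and ρ, not the direction. At 1.9 and 2.2 cm the direction drives most of the range.

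Hand check at 1.9 cm, decline prevented: difference 0.450 − 0.227 = 0.223; pooled share 0.338; SE = √(0.338 × 0.662 × 2/26) = 0.131; 0.223/0.131 = 1.70; Φ(1.70 − 1.96) ≈ 40%. This agrees with the simulation. At 2.2 cm with treatment raising TAPSE, the expected counts are only 26 × 0.067 = 1.7 and 26 × 0.017 = 0.4 patients, so the simulated 6% is used.

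**How far a fall registers in patients who start normal.** If every such patient falls by d, and ignoring measurement noise, the share reclassified is [Φ((1.6 + d − mean)/0.4) − Φ((1.6 − mean)/0.4)] / [1 − Φ((1.6 − mean)/0.4)].

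- d = 0.2 cm, mean 1.8: (0.500 − 0.309)/0.691 = 28%. At means of 2.0 and 2.2 it is 18% and 10%.
- d = 0.4 cm, mean 1.8: (0.691 − 0.309)/0.691 = 55%.

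**Unadjusted, like for like.** A cut keeps φ(c)²/[p(1 − p)] of the information, where p is the share below the cut c. With p = 50% that is 0.159/0.25 = 64%, a loss of about 36%. With 20%, 10% and 5% below the cut it keeps 49%, 34% and 22%.

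**The case against.** Several points on the other side stand. TAPSE is one component of one of six secondary endpoints, none of them powered. Every TAPSE input above is assumed, and the effect size favours the comparison: with a true difference of 0.10 cm, the analysis in centimetres itself detects it in only 19–32% of trials. Objective 2 speaks of change in each arm, while the power figures concern the contrast between arms, although section 11.2 does plan one. The trial is under way, with 60 enrolled and 28 having completed 6 months when section 11.1 was updated. Strain is categorised in the same sentence, so amending TAPSE alone leaves the same feature there.

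Three stronger readings are tempting, and the documents do not support them.

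- **That the endpoint is nearly blind in patients who start normal, so that a null result is uninformative in either direction.** This is exact for improvement. It is not so for decline, which is detected in about 28% of trials even at a mean of 2.2 cm.
- **That patients without carcinoid heart disease mostly start above the cut.** No baseline TAPSE values are given, and section 3.4 reports that "RV function is reduced in patients with intestinal carcinoid disease independent of obvious valvular involvement", without levels.
- **That change in centimetres will never be analysed.** Section 11.2 also summarises repeatedly measured variables by arm and visit, and its mixed model names no scale. An analysis in centimetres is not promised, but neither is it excluded.

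None of this supplies a reason for preferring the category, and the documents state none.

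**Conclusion.** The concern holds in a limited form. The endpoint as defined discards change in centimetres, and section 11.2 does not clearly restore it. That improvement cannot register from a normal start, and that a fall must cross 1.6 cm to count, needs no assumption.

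The category had lower power than the baseline-adjusted analysis in centimetres in every scenario run with a 0.25 cm difference. How much lower depends on the assumed distribution, on the baseline mean and on whether treatment raises TAPSE or prevents its decline. The figures illustrate the loss and do not estimate this trial's power. The change is worth making, but nothing here touches the primary endpoint or its sample size.

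**What to change.** Before unblinding, amend Objective 2c, secondary endpoint 2 and section 11.2 as follows:

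- Define the TAPSE endpoint as change from baseline in centimetres.
- Make the main analysis the comparison between arms at 6 months, adjusted for baseline TAPSE. All patients have an echo scheduled then.
- Report 3-month change for the CHD group of section 8.6 only, because the CS group has no echo at that visit. A repeated-measures model over both visits would otherwise carry data missing by design.
- Keep normal or abnormal at 1.6 cm as a descriptive shift table by arm.

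The cost is a small amendment to a secondary endpoint while the trial is running, which should be dated and recorded as made blind. It needs no new measurements, visits or patients.

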3.0 Background

3.1 Purpose

The basic hypothesis of our therapeutic programs in patients with carcinoid syndrome and carcinoid heart disease is to achieve meaningful and lasting symptom-improvement and look for responses to therapies that are associate with improved survival and favorable prognosis.

3.2 Historical Experience

Our group has a keen interest in the prevention, detection, and treatment of patients with carcinoid syndrome and those who develop carcinoid heart disease. Being part of MD Anderson Cancer Center, we have the unique advantage of having a robust GI medical oncology group and cardiology group that interact together and care for a significant number of patients with carcinoid syndrome and carcinoid heart disease. Most of these patients are treated with somatostatin analogs (SSA) therapy, but a significant portion have uncontrolled symptoms or develop carcinoid heart disease where medical therapy is limited and morbidity and mortality is extremely high.

3.3 Carcinoid Syndrome leading to Carcinoid Heart Disease: The role of Serotonin

Carcinoid tumors are rare neuroendocrine tumors (NETs) that can arise from enterochromaffin cells throughout the body. Some NETs are malignant and arise most commonly in the lung, rectum, and ileum (1). These malignant NETs metastasize to produce carcinoid syndrome. Patients with carcinoid syndrome present with vasomotor changes, diarrhea, hypotension, bronchospasm, and with carcinoid heart disease. A large portion of patients with carcinoid syndrome are thought to develop carcinoid heart disease. In fact, carcinoid heart disease is the initial presentation of carcinoid syndrome in up to 20% of patients and occurs in more than 50% percent of these patients (2, 3).

Carcinoid heart disease is a result of plaque-like deposits of fibrous tissue composed of smooth muscle cells, myofibroblasts, extracellular matrix, and an overlying endothelial layer. These fibrous deposits affect cardiac valves. This leads to stenosis and/or regurgitation of the valve, with regurgitation being more common. Patients with carcinoid heart disease present with symptoms in the fifth to seventh decades of life (13-15). Because the clinical manifestations of this disease are subtle early in its course, diagnosis of carcinoid heart disease requires a high suspicion. In fact, in one study 37% of patients had no clinical signs of cardiac abnormalities by physical exam and 27% of patients with moderate to severe tricuspid regurgitation were in New York Heart Association class 1 (13). There is also a significant time lag from onset of symptoms to the diagnosis of this disease, ranging from 2 to 5 years before diagnosis is confirmed. Patients usually present with fatigue and dyspnea. In those with disease progression, right-sided heart failure occurs with edema, ascites, and dyspnea (16-18).

It is believed that alterations in the metabolism of serotonin, its associated receptors, and a transporter gene are involved in the mechanisms of serotonin-induced carcinoid heart disease (4, 5). Furthermore, indirect evidence of higher serotonin levels in patients with known carcinoid heart disease than in patients without carcinoid heart disease points to a role for high serotonin levels as a likely contributor to the development of carcinoid heart disease (6-8). More recently, researchers have implicated roles for serotonin and 5-hydroxytryptamine receptors in the development of valve disease. The activation of 5-hydroxytryptamine 2B receptors via expression of the tyrosine kinase SRC and mediation by transforming growth factor B1 promotes myofibroblast deposition and infiltration and activation of valvular interstitial cells, leading to fibrosis of the valves (5, 9-12).

3.4 Biomarkers in Carcinoid Heart Disease and Carcinoid Syndrome

While clinical signs maybe difficult to assess the role of the cardiac biomarkers has been studied and utilized in both patient with carcinoid heart disease and carcinoid syndrome. Patients with normal NT-proBNP levels have a better survival when they have carcinoid syndrome irrespective of whether or not they have carcinoid heart disease (17). Furthermore, NT-pro-BNP and 5-HIAA levels are independently associated with

symptom status and mortality in patients with metastatic NETs and carcinoid heart disease (26).

Patients with carcinoid heart disease in general have elevated NT-proBNP levels (Median 1,149 pg/ml vs 101 pg/ml) (18) highlighting the prognostic implications of this cardiac biomarker. Lastly, an NT-proBNP level cutoff of 260 pg/ml provides a high sensitivity (92%) and specificity (91%) to detect carcinoid heart disease (18). In fact this NT-ProBNP levels cutoff is being advocated in the Carcinoid Heart Disease expert statement for the screening and investigation of carcinoid heart disease (19).

As serotonin levels are implicated in both carcinoid syndrome and carcinoid heart disease, urinary 5-HIAA levels are also associated with the disease. In fact, a Urinary 5-HIAA level of $>300 \mu\text{mol}/24 \text{ hours}$ is associated with a 2.74-fold increase of the development and progression of carcinoid heart disease (20).

Furthermore, a novel echocardiographic technique, myocardial strain analysis, has some promising applications in patients with carcinoid disease. In a study using the RV free wall strain and tricuspid annular plane systolic excursion (TAPSE), it has been demonstrated that RV function is reduced in patients with intestinal carcinoid disease independent of obvious valvular involvement. This finding, in addition to the fact that patients with and without carcinoid heart disease showed slightly but significantly reduced LV global strain compared with healthy individuals, would suggest that that intestinal carcinoid disease may affect cardiac function before valvular involvement (25) and perhaps the possible role of serotonin in this process.

3.5 Cardiac Imaging in Carcinoid Disease and Carcinoid Heart Disease

Echocardiography has been the mainstay of evaluation of patients with carcinoid heart disease and is in fact recommended as a screening and investigational tool (19).

Furthermore, a novel echocardiographic technique, known as myocardial strain analysis has some promising applications in patients with carcinoid disease. In a study using the RV free wall strain and tricuspid annular plane systolic excursion (TAPSE), it has been demonstrated that RV function is reduced in patients with intestinal carcinoid disease independent of obvious valvular involvement. This finding, in addition to the fact that patients with and without carcinoid heart disease showed slightly but significantly

reduced LV global strain compared with healthy individuals, would suggest that that intestinal carcinoid disease may affect cardiac function before valvular involvement (25) and perhaps the possible role of serotonin in this process.

3.6 Proposed Therapy with Telotristat Ethyl (XERMELO)

In this trial, we propose to use of telotristat ethyl in patients with carcinoid syndrome and carcinoid heart disease. We know that 5-HIAA and serotonin are implicated in both carcinoid syndrome and carcinoid heart disease. We know that telotristat ethyl works with SSA therapy to reduce hormone overproduction and control carcinoid syndrome diarrhea. We also know that the cardiac biomarker NT-proBNP provides prognostic information in these patients. In this study we propose that by using telotristat ethyl in conjunction with a SSA versus SSA alone, that telotristat ethyl will have a positive effect on hormone production and will demonstrate biochemical response in patients with known carcinoid syndrome and/or carcinoid heart disease.

